#### 8.2. Patient Exclusion Criteria

All patients with any of the following conditions or characteristics must be excluded from the study:

- Prior exposure to bardoxolone methyl;
- Kidney or other solid organ transplant recipient or a planned transplant during the study;
- 3. B-type natriuretic peptide (BNP) level >200 pg/mL at Screen A visit;
- Acute dialysis or acute kidney injury within 12 weeks prior to Screen A visit or during Screening;
- Serum albumin < 3 g/dL at Screen A visit;

- 6. Systemic immunosuppression for more than 2 weeks, cumulatively, within the 12 weeks prior to randomization or anticipated need for immunosuppression during the study. Patients with IgAN or FSGS that are receiving prednisone at doses ≤ 10 mg/day are eligible for enrollment in the IgAN or FSGS cohorts, but doses must be stable for 30 days prior to Screen A visit and should be anticipated to remain the same throughout the study. Refer to Section 9.3.1 for additional details;
- For patients enrolling in IgAN Cohort:
  - Systemic manifestations of Henoch-Schonlein purpura within 1 year prior to Screen A visit;
  - Have used belimumab, eculizumab, or rituximab within 6 months prior to Screen A visit;
- For patients enrolling in ADPKD Cohort:
  - Receiving tolvaptan;
- Cerebrovascular event (stroke, transient ischemic attack) or aneurysm within 6 months prior to Screen A visit or during Screening;
- 10. History of clinically significant left-sided heart disease and/or clinically significant cardiac disease, including but not limited to any of the following:
  - Clinically significant congenital or acquired valvular disease;
  - b. Left ventricular ejection fraction < 40% (based on echocardiogram performed at Screen A visit or within 6 months prior to Day 1);
  - Pericardial constriction (based on echocardiogram performed at Screen A visit or within 6 months prior to Day 1);
  - Restrictive or congestive cardiomyopathy (based on echocardiogram performed at Screen A visit or within 6 months prior to Day 1);

- e. Symptomatic coronary disease (prior myocardial infarction, percutaneous coronary intervention, coronary artery bypass graft surgery, or angina);
- History of hospitalization for heart failure;
- g. Cardiac insufficiency, defined as New York Heart Association Class >2;
- History of atrial fibrillation;
- History of unstable arrhythmias;
- 11. Uncontrolled systemic hypertension as evidenced by sitting systolic blood pressure (BP) > 160 mm Hg or sitting diastolic BP > 100 mm Hg at Screen A visit after a period of rest;
- Systolic BP < 90 mm Hg at Screen A visit after a period of rest;

- History of malignancy within 2 years prior to Screen A visit, with the exception of localized skin or cervical carcinomas;
- Uncontrolled diabetes (HbA1c > 10.0%) at Screen A visit;
- Untreated or uncontrolled active bacterial, fungal, or viral infection;
- 16. Participation in other interventional clinical studies within 30 days prior to Day 1;
- 17. Unwilling to practice acceptable methods of birth control (both males who have partners of childbearing potential and females of childbearing potential) during Screening, while taking study drug, and for at least 30 days after the last dose of study drug is ingested;
- Women who are pregnant or breastfeeding;
- Known hypersensitivity to any component of the study drug;
- Any abnormal laboratory level that, in the opinion of the investigator, would put the patient at risk by trial enrollment;
- Patient is, in the opinion of the investigator, unable to comply with the requirements of the study protocol or is unsuitable for the study for any reason;

# 8.3. Screening Period

The screening period must not exceed 6 months. The Screen B visit should be no more than 30 days prior to Day 1.

# 8.4. Patient Re-Screening

Patients that screen fail may repeat the Screening procedures to qualify for the study with approval from the medical monitor.

## 8.5. Patient Discontinuation and Termination

Patients have the right to discontinue study drug or withdraw from the study at any time for any reason, without prejudice to their medical care. Furthermore, the investigator may discontinue a patient from study drug. Consultation with the medical monitor should occur prior to study drug discontinuation or withdrawing a patient from the study. The reason for a patient's

discontinuation from study drug or study termination will be recorded in the electronic case report form (eCRF).

#### 8.5.1. Patient Discontinuation Criteria

Discontinuation refers to a patient's stopping administration of study drug. Reasons for study drug discontinuation may include the following:

- Occurrence of an AE or change in medical status that leads the investigator to be concerned about the patient's welfare
- Administrative reasons (e.g., inability to continue)
- Sponsor termination of the study
- Voluntary withdrawal
- Females who become pregnant during the study

Patients must discontinue study drug if any of the following occur.

- ALT or AST > 8X ULN;
- ALT or AST > 5X ULN for more than two weeks;
- ALT or AST > 3X ULN and (total bilirubin > 2X ULN or INR > 1.5);
- ALT or AST > 3X ULN with the appearance of fatigue, nausea, vomiting, right upper quadrant pain or tenderness, fever, rash, and/or eosinophilia (> 5%).

Patients who are discontinued from study drug should still continue in the study, complete all study visits, and undergo all scheduled study assessments, if possible.

#### 8.5.2. Patient Termination Criteria

Termination refers to a patient's stopping study drug and all study assessments and visits. Reasons for study termination include the following:

- Loss to follow-up
- Death
- Withdrawal of consent

Every reasonable effort should be made to contact patients who do not return for a scheduled visit. The investigator should inquire about the reason for withdrawal, request the patient return all unused investigational product, request the patient return for end-of-treatment and follow-up visits (if applicable), and follow-up with the patient regarding any unresolved AEs.

## 9. TREATMENT OF PATIENTS

## 9.1. Select Management Guidelines

The following guidelines apply to the management of study participants:

## 9.1.1. Management of Fluid Status

Specific risk mitigation procedures will be employed to reduce the potential for bardoxolone methyl-induced fluid overload. These procedures include exclusion of patients with any severe renal disease, defined as an eGFR value of < 30 mL/min/1.73 m^2. To exclude patients with significant cardiac dysfunction, the study will exclude patients with a history of left-sided heart disease. Patients who have evidence of volume overload at baseline, defined as BNP level of > 200 pg/mL, will also be excluded.

Laboratory data will also be used to monitor fluid status after randomization. Patients that experience a BNP > 100 pg/mL that represents a doubling (or more) of BNP levels from Day 1 should be instructed to stop taking their study medication immediately and return to the clinic within 1 week (± 3 days) for an unscheduled physical examination and laboratory assessment by the investigator.

Additionally, after randomization patients will be closely monitored for rapid weight gain suggestive of fluid overload. Patients will be given a Sponsor-provided scale to use at home to collect and record their weights daily during the first 8 weeks of the treatment period and weekly thereafter. Patients who experience a five-pound (2.3 kilogram) or greater increase in weight since their Day 1 weight during the first 8 weeks will be instructed to stop taking their study medication immediately and return to the clinic for an unscheduled physical examination and laboratory assessment by the investigator.

Investigators are encouraged to start or increase doses of diuretics (thiazides, loop diuretics) early after recognition of edema. This can be done concurrently with temporary drug discontinuation and re-initiation. Patients may not restart their study medication until the investigator has completed and documented an assessment of fluid overload.

Patients who experience a five-pound (2.3 kilogram) or greater increase in weight after the Week 8 study visit will be instructed to return to the clinic for an unscheduled physical examination and laboratory assessment by the investigator. Study medication should not be discontinued until the investigator has completed and documented an assessment of fluid overload.

Investigators should advise patients to watch for signs and symptoms of fluid overload. Patients should be informed to notify their physicians immediately if they experience swollen feet, chest pain, shortness of breath with mild exertion or while lying down, or other relevant symptoms. The investigator should immediately assess symptoms of fluid overload and determine appropriate medical management, as necessary, including whether stopping drug administration is required. At the earliest sign of worsening or new onset peripheral edema or other signs and symptoms of acute volume overload, investigators will be expected to report if changes to a patient's diuretic regimen have been required to manage edema.

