#### Major exclusion criteria:

- Prior exposure to bardoxolone methyl;
- 2. Kidney or any other solid organ transplant recipient or a planned transplant during the study;
- B-type natriuretic peptide (BNP) level > 200 pg/mL at Screen A visit;
- Acute dialysis or acute kidney injury within 12 weeks prior to Screen A visit or during Screening;
- Serum albumin < 3 g/dL at Screen A visit;

- 6. Systemic immunosuppression for more than 2 weeks, cumulatively, within the 12 weeks prior to randomization or anticipated need for immunosuppression during the study. Patients with IgAN or FSGS that are receiving prednisone at doses ≤ 10 mg/day are eligible for enrollment in the IgAN or FSGS cohorts, but doses must be stable for 30 days prior to Screen A visit and should be anticipated to remain the same throughout the study. Refer to Section 9.3.1 for additional details:
- 7. For patients enrolling in IgAN Cohort:
  - Systemic manifestations of Henoch-Schonlein purpura within 1 year prior to Screen A visit;
  - Have used belimumab, eculizumab, or rituximab within 6 months prior to Screen A visit:
- 8. For patients enrolling in ADPKD Cohort:
  - Receiving tolvaptan;
- Cerebrovascular event (stroke, transient ischemic attack) or aneurysm within 6 months prior to Screen A visit or during Screening;
- 10. History of clinically significant left-sided heart disease and/or clinically significant cardiac disease, including but not limited to any of the following:
  - a. Clinically significant congenital or acquired valvular disease;
  - b. Left ventricular ejection fraction < 40% (based on echocardiogram performed at Screen A visit or within 6 months prior to Day 1);
  - Pericardial constriction (based on echocardiogram performed at Screen A visit or within 6 months prior to Day 1);
  - Restrictive or congestive cardiomyopathy (based on echocardiogram performed at Screen A visit or within 6 months prior to Day 1);
  - e. Symptomatic coronary disease (prior myocardial infarction, percutaneous coronary intervention, coronary artery bypass graft surgery, or angina);
  - History of hospitalization for heart failure;
  - g. Cardiac insufficiency, defined as New York Heart Association Class > 2;
  - History of atrial fibrillation;
  - History of unstable arrhythmias;
- 11. Uncontrolled systemic hypertension as evidenced by sitting systolic blood pressure (BP)
   160 mm Hg or sitting diastolic BP > 100 mm Hg at Screen A visit after a period of rest;

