#### 5.1.2.1. Fluid Overload

Similar to endothelin receptor antagonists (ERAs) in certain patient populations, including bosentan in advanced congestive heart failure and avosentan in advanced CKD, bardoxolone methyl treatment was found to be associated with an increased risk for fluid overload and heart failure hospitalizations in the BEACON trial, which enrolled patients with Stage 4 CKD (eGFR 15 to 29 mL/min/1.73 m²) and type 2 diabetes. The overall increased risk for fluid overload and heart failure events with bardoxolone methyl appeared to be limited to the first three to four weeks after initiation of treatment. Elevated BNP and prior hospitalization for heart failure were identified as risk factors that contributed to increased risk for these events. The increased risk for these events from bardoxolone methyl treatment had not been observed in six previous CKD studies, which were conducted mostly in patients with Stage 3b CKD (eGFR of 30 to 44 mL/min/1.73 m²), patients with hepatic dysfunction, cancer patients, or healthy volunteers.

Review of admission notes and narrative descriptions for heart failure hospitalizations in BEACON indicates that heart failure in bardoxolone methyl-treated patients was often preceded by rapid fluid weight gain (several kilograms within the first weeks of treatment initiation) and was not associated with acute renal decompensation or acutely reduced left ventricular contractility. Available data from BEACON and other studies suggest that bardoxolone methyl treatment can differentially affect hemodynamic status according to the clinical condition of patients and likely promotes fluid retention in patients with more advanced renal dysfunction and other recognized risk factors associated with heart failure at baseline.

In a Phase 2 dose-ranging study of the efficacy and safety of bardoxolone methyl in patients with pulmonary hypertension (LARIAT), risk mitigation procedures were employed to reduce the potential for bardoxolone methyl-induced fluid overload; these procedures excluded patients with the identified risk factors and ensured close monitoring for fluid retention within the first month of treatment. To date, the risk for acute fluid overload AEs with bardoxolone methyl in late-stage CKD patients has not been observed in PH patients.

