- e Screening eligibility procedures do not need to be repeated on Day 1; however, a review of any changes in eligibility criteria should be evaluated prior to Day 1 procedures, and a urine pregnancy test should be performed for WOCBP.
- f An echocardiogram performed at the Screen A visit or within 6 months prior to Day 1 may be used to determine eligibility.
- g A serum pregnancy test will be performed at the Screen A visit for WOCBP or at any point in time if a pregnancy is suspected. All other pregnancy assessments will be urine pregnancy tests.
- h AE assessments on Day 1 should be performed following study drug administration.
- Only patients enrolling in the IgA nephropathy cohort or the FSGS cohort are required to have a kidney biopsy. Patients with definitive diagnosis of IgA nephropathy or FSGS from previous biopsy will not have a kidney biopsy as part of the study, but must provide diagnosis documentation from previous kidney biopsy for eligibility.
- j Only patients enrolling in the T1D cohort are required to have fasting C-peptide levels assessed. Patients should be instructed to fast prior to study visit.
- k Only patients enrolling in the ADPKD disease cohort are required to have genetic testing. Patients with confirmed PKD1 mutations from previous genetic testing will not have genetic testing performed as part of the study, but must provide documentation of genetic mutation for eligibility.
- Albumin to creatinine ratio will be measured by first morning void spot urine collection. Appropriate containers for the collection will be provided to the patient at the visit prior to collection.
- mPatients must be instructed to not take their study drug prior to coming to the clinic for visits when PK samples will be collected. Patients must administer the study drug dose in the clinic on PK sample collection visits after the 0 hour PK blood sample is collected. Patients will have blood samples for PK analysis drawn just prior to (0 hour) and after (2 and 4 hours) dose administration.

Abbreviations: EoT= end-of-treatment; ECG = electrocardiogram, F/U = follow-up; PK = pharmacokinetic, WOCBP = women of child-bearing potential

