## 8. SELECTION AND WITHDRAWAL OF PATIENTS

#### 8.1. Patient Inclusion Criteria

Diagnosis and main criteria for inclusion:

- Male and female patients 18 ≤ age ≤ 60 upon study consent;
- Screening eGFR (average of Screen A and Screen B eGFR values) ≥ 30 and ≤ 90 mL/min/1.73 m². The two eGFR values collected at Screen A and Screen B visits used to determine eligibility must have a percent difference ≤ 25%;
- Albumin to creatinine ratio (ACR) ≤ 2500 mg/g at Screen B visit;
- 4. If receiving an angiotensin converting enzyme (ACE) inhibitor and/or an angiotensin II receptor blocker (ARB), patients should be prescribed the maximally tolerated labeled daily dose (MTLDD), as defined in Section 9.1.7, for at least 6 weeks prior to the Screen A visit. The dosage of ACE inhibitor and/or ARB should remain the same throughout the remainder of the study (i.e., no change in dosage or medication), and any potential changes should be discussed with the medical monitor. Patients not taking an ACE inhibitor and/or ARB because of a medical contraindication may be eligible if they have discontinued treatment at least 8 weeks prior to the Screen A visit (these patients must be discussed with the medical monitor prior to enrollment);
- For patients enrolling in T1D Cohort:
  - Diagnosis of type 1 diabetes confirmed by fasting C-peptide level. Diagnosis must have been made ≤ 35 years of age;
  - Prescribed stable dose of insulin to maintain adequate glucose control for at least 6 months prior to the Screen A visit;
- For patients enrolling in IgAN Cohort:
  - Biopsy-confirmed IgA nephropathy;
- For patients enrolling in FSGS Cohort:
  - Biopsy-confirmed FSGS that is not due to known secondary causes including morbid obesity, decreased renal mass, viral infections, drug-induced nephrotoxicity, or prior history of vasculitis;
- For patients enrolling in ADPKD Cohort:
  - Genetic confirmation of PKD1 mutation;
- Adequate bone marrow reserve and organ function at the Screen A visit as follows:
  - Hematologic: Absolute neutrophil count > 1.5 x 10^3/L, platelets > 100 x 10^3/L, hemoglobin (Hgb) ≥ 9 g/dL;
  - b. Hepatic: Total bilirubin (TBL) ≤ 1.5X the upper limit of normal (ULN), alanine aminotransferase (ALT) and aspartate aminotransferase (AST) ≤ 1.5X ULN;
- Able to swallow capsules;

- Willing and able to comply with scheduled visits, treatment plan, laboratory tests, and other study procedures;

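### Section 9.1.1 excludes on BNP at baseline, but the BNP criterion tests only Screen A, which can precede first dose by up to 6 months

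*Protocol*

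**What the plan says.** - Protocol section 9.1.1 describes three exclusions meant to lower the risk of drug-induced fluid overload: low eGFR, left-sided heart disease, and raised BNP. The third reads: "Patients who have evidence of volume overload at baseline, defined as BNP level of > 200 pg/mL, will also be excluded".
- Criterion 3 in Protocol section 8.2 excludes on "B-type natriuretic peptide (BNP) level >200 pg/mL at Screen A visit". The synopsis gives the same limit and the same visit: "B-type natriuretic peptide (BNP) level > 200 pg/mL at Screen A visit".
- Protocol section 8.3 says: "The screening period must not exceed 6 months". It places Screen B no more than 30 days before Day 1.
- Protocol Table 5 schedules BNP at Screen A, on Day 1, and at Weeks 1, 2, 4, 6, 8, 12 and 16, but not at Screen B. Day 1 procedures come before the first dose.
- Footnote e to that table says: "Screening eligibility procedures do not need to be repeated on Day 1". The same sentence goes on to ask for a review of changes in eligibility before the Day 1 procedures.
- Exclusions 20 and 21 let the investigator exclude a patient for a laboratory abnormality judged to pose a risk, or as unsuitable for any reason.
- SAP section 7.2 takes baseline, unless otherwise specified, as the last available value before first dose. No exception is given for BNP.
- SAP Table 3 gives Screen A a target of Day -60 and a window of Day -180 to -2.

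**The concern.** The safeguard in section 9.1.1 and the criterion that should carry it out name different measurements. One refers to the patient's state at baseline, the other to a visit that can lie months earlier. A site that follows the criteria exactly can dose a patient whom section 9.1.1 says is excluded.

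This matters because of the protocol's own account of the drug's main safety issue. On fluid overload and heart failure events, section 5.1.2.1 says: "Elevated BNP and prior hospitalization for heart failure were identified as risk factors that contributed to increased risk for these events". It adds that the excess risk appeared confined to the first three to four weeks of treatment. BNP status near the first dose is therefore the relevant quantity, and that is the quantity the criterion does not control.

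**Working it through.** The plan states no figure on this point. The check sets the texts side by side and adds simple arithmetic.

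**1. Which sample each text refers to**

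| Source | Sample | Latest time before first dose |
|---|---|---|
| Protocol 9.1.1 | Baseline (undefined for BNP in the protocol; under SAP 7.2 the last pre-dose value, normally Day 1) | Normally Day 1, pre-dose |
| Protocol 8.2 and synopsis, criterion 3 | Screen A | Up to 6 months earlier |
| Table 5, Screen B | None drawn | Not applicable |
| Table 5, Day 1 | Drawn pre-dose, tied to no criterion | Day 1 |

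**2. Length of the gap**

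- Longest, by the SAP window: 180 days, and 180 / 7 = 25.7 weeks. This agrees with the protocol's 6 months.
- At the SAP target: 60 days, and 60 / 7 = 8.6 weeks.
- Screen B, for comparison: at most 30 days, and 30 / 7 = 4.3 weeks.

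**3. Does anything mandatory close the gap?**

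- Table 5 marks an inclusion/exclusion review on Day 1. Criterion 3 names Screen A, so reviewing it again on Day 1 gives the same answer whatever the current BNP.
- Footnote e places the review of changes before the Day 1 procedures, and so before the Day 1 BNP is drawn.
- Exclusions 20 and 21 could remove the patient, but they set no BNP limit and require no BNP result after Screen A.
- Protocol section 9.10.21 refers to storage and shipment of the sample but gives no turnaround time. Whether a Day 1 result could be known before dosing is therefore an assumption either way.

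**4. Illustration (invented values)**

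Take BNP of 150 pg/mL at Screen A and 260 pg/mL on Day 1.

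- Criterion 3: 150 is not above 200, so the patient is not excluded.
- Section 9.1.1 as worded: 260 is above 200, and 260 / 200 = 1.3 times the limit, so the patient is excluded.

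**5. Effect on the on-treatment BNP rule**

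Section 9.1.1 acts on a BNP above 100 pg/mL that is at least twice the Day 1 value. For the patient above, 2 × 260 = 520 pg/mL. Any patient above 200 pg/mL on Day 1 meets the rule only above 2 × 200 = 400 pg/mL.

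**The case against.** The strongest reply is that the opening of section 9.1.1 is a loose summary. It also gives the eGFR limit without naming a visit and shortens the cardiac exclusion. The synopsis and section 8.2 agree on Screen A, and the definition of baseline as the last pre-dose value comes from the SAP, where it serves analysis. That may well explain how the mismatch arose. It does not remove it: baseline is still the wrong word for a sample that may be 6 months old. Other criteria do reach past Screen A. Acute kidney injury and cerebrovascular events are covered throughout screening, eGFR uses both screening visits, and ACR uses Screen B.

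The second reply is that other safeguards remain, and this stands. The Day 1 visit includes a physical examination, vital signs and weight before dosing. Afterwards there are daily home weights for 8 weeks with a 2.3 kg rule, symptom reporting, telephone calls on Days 3, 10 and 21, and visits at Weeks 1, 2 and 4. These cover the stated risk period, and the weight rule does not depend on BNP. They act after dosing, however, and do not deliver the pre-dose exclusion that section 9.1.1 describes.

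The third reply is that the excess risk was seen in a trial at eGFR 15 to 29, and not in six earlier CKD studies conducted mostly at 30 to 44; this trial requires at least 30. That is fair and limits the likely harm. Section 5.1.2.1 also reports no such risk so far in pulmonary hypertension, but under procedures that excluded patients with the identified risk factors.

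A reader might also infer that the albumin, bilirubin and ALT/AST limits share the defect, because they too are tied to Screen A ("Serum albumin < 3 g/dL at Screen A visit"; "Adequate bone marrow reserve and organ function at the Screen A visit as follows"). The documents do not support that. No text says those limits hold at baseline, and the synopsis agrees with sections 8.1 and 8.2. Applying them later would be a preference, not the repair of a contradiction.

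**Conclusion.** The inconsistency is real and concerns a safety eligibility rule for a risk factor the protocol itself names. A patient above 200 pg/mL at baseline is not excluded by the BNP criterion and can be dosed, subject to the investigator's discretion.

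Its size is bounded as follows. The qualifying BNP can be up to about 180 days old, but that is the maximum; the SAP target implies about 60 days. The documents give no figure for how many patients would cross the limit between Screen A and Day 1, so no frequency can be stated.

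Two stronger readings should be avoided. A reader might infer that such a patient is necessarily admitted; exclusions 20 and 21 and the Day 1 review mean only that the BNP criterion does not stop them. A reader might also infer an effect on efficacy conclusions; nothing here touches the primary eGFR analysis or the power statement.

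The conclusion assumes that baseline in section 9.1.1 means a value at or near first dose, as SAP section 7.2 would have it. If the sponsor meant Screen A, the fault is one of wording, but the text still needs correcting.

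**What to change.** Reconcile section 9.1.1, section 8.2, the synopsis and Table 5 so that the BNP exclusion, its time point and the sampling schedule agree. Which time point is intended is for the sponsor to state.

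- If Screen A is intended, section 9.1.1 should name Screen A and stop referring to baseline. This is a text change only.
- If section 9.1.1 is intended as written, the existing limit has to be tied to a BNP result available close to and before first dose. One route is a sample at the Screen B blood draw that already takes place. That would shorten the longest gap from about 180 to 30 days (180 / 30 = 6 times shorter). It costs one extra tube and possibly more screen failures, whose number cannot be estimated from the documents. It would still not be a Day 1 value: a patient at 150 pg/mL at Screen B and 260 pg/mL on Day 1 would still pass, so section 9.1.1 would need to name the visit.
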